6.5 CONCOMITANT THERAPY

All concomitant medications and interventions are permissible during the study. Data on concomitant antimicrobial therapy administered at the time of thoracostomy tube placement will be collected. Antimicrobial agents include antibacterial, antiviral, antifungal, and anti-parasitic medications.

7 STUDY INTERVENTION DISCONTINUATION AND PARTICIPANT DISCONTINUATION/WITHDRAWAL

7.1 DISCONTINUATION OF STUDY INTERVENTION

If the initial thoracostomy tube has inadequate drainage, the primary care team reserves the right to replace the tube. The patient will not be removed from the study and this data will be collected as an outcome.

7.2 PARTICIPANT DISCONTINUATION/WITHDRAWAL FROM THE STUDY

Participants will be informed at the time of consent that they are free to withdraw from the study at any time and for any reason. They will be assured that their medical care will not be affected should they elect to discontinue participation in the study. The date the patient has withdrawn from the study will be recorded.

7.3 LOST TO FOLLOW-UP

At Day 90 a telephone call will be made to the participant to assess outcome. Three attempts will be made to establish contact. If contact is not achieved, the electronic medical record will be the only source used to complete the data set.

8 STUDY ASSESSMENTS AND PROCEDURES

8.1 EFFICACY ASSESSMENTS

The rates of failure of drainage (primary outcome) will be estimated as proportions and compared between the two groups using a Chi-square test corrected for the non-inferiority hypothesis. The margin of non-inferiority is defined as of 8%.

8.2 SAFETY AND OTHER ASSESSMENTS

The PI and the study team will meet biweekly to review the study procedures, enrollment (screening and randomization), implementation, protocol deviations, data collection, and adverse events. The biostatistics team will generate monthly reports for the study team which will monitor screening, enrollment, completeness of data for intervention implementation and outcomes, adverse events, and protocol deviations.

A medical monitor will determine the course of action necessary to meet safety goals and objectives. After the first 20 patients are enrolled and randomized, the study statisticians will generate a safety report for medical monitor review. An interim analysis for inferiority at 50% and 75% information accrual (see section 9.4.4: Planned Interim Analysis) will also be conducted. The medical monitor will recommend stopping if there is an increased incidence of procedure related serious complications or deaths in either treatment group that is found to be clinically significant.

Safety endpoints assessed by the study team and medical monitor will include:

- General safety assessments
 - Incidence of unanticipated serious adverse events related to chest tube size
- Thoracostomy tube related safety events
 - Hemodynamic instability post-insertion
 - Need for additional interventions (VATS, thoracotomy, chest tube replacement)
 - Procedure related deaths
 - Empyema
 - Re-accumulation/Recurrent pneumo- or hemothorax
 - Readmission to hospital within 90 days of insertion

8.3 ADVERSE EVENTS AND SERIOUS ADVERSE EVENTS

8.3.1 DEFINITION OF ADVERSE EVENTS (AE)

An adverse event (AE) is any untoward or unfavorable medical occurrence in a human subject temporally associated with the use of a medical treatment or procedure that may or may not be related to the use of the medical treatment or procedures.

In this study, we will not be recording AEs unrelated to thoracostomy tube size, as both of the thoracostomy tubes used in this study are being used within their approved indications.

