2.3 RISK/BENEFIT ASSESSMENT

2.3.1 KNOWN POTENTIAL RISKS

Some risks from the insertion procedure are:

- Bleeding or infection where the tube is inserted
- Improper placement of the tube (into the tissues, abdomen, or too far in the chest)
- Injury to the lung
- Injury to organs near the tube, such as the spleen, liver, stomach, heart, or diaphragm
- Infection

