8.3.2 DEFINITION OF SERIOUS ADVERSE EVENTS (SAE)

A serious adverse event (SAE) is an AE occurring during any study phase (i.e., treatment, follow-up), that results in one or more of the following:

- Death
- Life-threatening adverse event
- Inpatient hospitalization or prolongation of existing hospitalization
- Persistent or significant incapacity or disruption of the ability to conduct normal life functions
- Congenital anomaly/birth defect
- An important medical event that may not result in death, be life-threatening, or require hospitalization but may be considered serious when, based upon appropriate medical judgment, they may jeopardize the patient or subject and may require medical or surgical intervention to prevent one of the outcomes listed above.

In this study, we will only be reporting SAEs that are determined to be unexpected and possibly, probably, or definitely related to the size of the initial thoracostomy tube. The principal investigator will assess all potential adverse events for this criteria.

SAEs will be reported in the manner and timeframe that is outlined in the Chesapeake IRB handbook.

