8.3.4 RELATIONSHIP TO STUDY INTERVENTION

The principle investigator will assess the relationship of an adverse event to the thoracostomy tube insertion procedure or tube size will be the according to the following definitions:

Unrelated	There is no evidence of any causal relationship
Possibly related	There is some evidence to suggest a causal relationship. However, the influence of other factors may have contributed to the event.
Probably related	There is evidence to suggest a causal relationship and the influence of other factors is unlikely
Definitely related	There is clear evidence to suggest a causal relationship and other possible contributing factors can be ruled out.

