8.3.7 SERIOUS ADVERSE EVENT REPORTING

Participants will be monitored for serious adverse events from the moment of randomization through 90 days post tube insertion. Due to their mechanism of injury and high trauma burden, participants are expected to have significant trauma related complications. AEs or SAEs determined to be unrelated to study procedure or tube size will not be reported to the IRB. Submission of any serious adverse event will not occur until relatedness of the event has been determined.

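### AE recording is limited to events judged related to tube size, while the monitor's criterion concerns the procedure; by-arm counts of insertion bleeding and organ injury may be incomplete

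*Combined protocol and SAP*

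**What the plan says.** Aim I in section 3 covers safety as well as efficacy, so the by-arm safety comparison is part of the trial's stated purpose. Five places bear on which events enter it.

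- **Recording (8.3.1).** "we will not be recording AEs unrelated to thoracostomy tube size". The reason given is that both tubes are used within their approved indications.
- **SAE reporting (8.3.2).** The study will "only be reporting SAEs that are determined to be unexpected and possibly, probably, or definitely related to the size of the initial thoracostomy tube". On who decides: "The principal investigator will assess all potential adverse events for this criteria".
- **Relatedness scale (8.3.4).** The principal investigator rates the "relationship of an adverse event to the thoracostomy tube insertion procedure or tube size".
- **IRB reporting (8.3.7).** "AEs or SAEs determined to be unrelated to study procedure or tube size will not be reported to the IRB".
- **Monitoring (8.2).** "The medical monitor will recommend stopping if there is an increased incidence of procedure related serious complications or deaths in either treatment group", if the increase is judged clinically significant. No numerical boundary is given.

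The known risks in 2.3.1 include bleeding at the insertion site, injury to the lung, and "Injury to organs near the tube, such as the spleen, liver, stomach, heart, or diaphragm".

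**The concern.** The recording rule and the monitoring criterion do not have the same scope. A complication of insertion that the principal investigator regards as unrelated to tube size falls inside the 8.2 criterion and outside the 8.3.1 recording rule.

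The filter also asks for a judgement that can rarely be made in one patient. Whether a smaller or larger tube changes the risk of bleeding or organ injury is what the randomised comparison should show. If events are kept or dropped on a case-by-case view of that same question, the comparison is partly decided before the arms are counted. The judgement requires knowledge of the tube used, whereas the synopsis says that staff collecting and recording data are masked to it.

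At stake are the Aim I safety comparison and the counts on which the medical monitor relies.

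**Working it through.** No figure in the plan measures this point, so the main check sets the sections side by side.

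**Step 1. Scope of each rule**

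| Section | Purpose | Scope |
|---|---|---|
| 8.3.1 | recording of AEs | tube size only |
| 8.3.2 | reporting of SAEs | unexpected, and at least possibly related to tube size |
| 8.3.4 | relatedness scale | insertion procedure or tube size |
| 8.3.7 | reporting to the IRB | study procedure or tube size |
| 8.2 | monitor's criterion | procedure |

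The only rule on recording is narrower than the criterion that depends on it.

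**Step 2. Do the known risks in 2.3.1 have an item of their own?**

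| Risk | 6.2 daily log | 8.2 safety list | Schedule of Activities |
|---|---|---|---|
| Bleeding at the site | no (drainage volume only) | no | no |
| Infection | yes | empyema | empyema |
| Improper placement | yes | only through tube replacement | yes |
| Injury to the lung | no (air leak is an indirect sign) | no | no (air leak only) |
| Injury to nearby organs | no | no | no |

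The schedule has a general AE/SAE row, but 8.3.1 governs what is entered there. The general item in 8.2 is again limited to unanticipated serious events related to tube size.

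**Step 3. Indirect routes.** Several outcomes are collected whatever the attribution: instability after insertion, VATS or thoracotomy, additional or replacement tubes, infection, readmission and death (4.1, 6.2, 8.2, 8.3.5, Schedule of Activities). An injury leading to one of these leaves a trace, with limits:

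- Vital signs are scheduled 5 minutes before and after insertion, so later bleeding may not show.
- The schedule's footnote on operative data names VATS, thoracotomy and tube replacement. Section 4.1 gives VATS only as an example, but no item names an abdominal operation.
- No item records insertion injury as the reason for an operation or readmission. Section 8.3.7 itself expects a heavy load of trauma complications in these patients.

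What remains is an event that is judged procedure-related but not size-related and leads to no listed outcome, or one whose listed outcome is recorded without the injury as its cause.

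**Step 4. Scale, on assumed rates.** The arm size is 126 (section 9.2). It reproduces with 7% failure in both arms, margin 8%, one-sided α = 0.05 and power 80%: n = (1.645 + 0.842)² × 2 × 0.07 × 0.93 / 0.08² ≈ 125.8, rounded up to 126. The documents give no rate for insertion bleeding or organ injury. Expected events per arm = 126 × assumed rate:

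- 1%: 126 × 0.01 = 1.3
- 2%: 126 × 0.02 = 2.5
- 5%: 126 × 0.05 = 6.3

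The expected primary failures are 126 × 0.07 = 8.8 per arm. The counts above are all such events, serious or not. Only the part left over in step 3 is exposed to the filter.

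**Step 5. What incomplete recording could do, also on assumed rates**

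- *Equal loss in both arms.* Take true rates p₁ = 2% and p₂ = 8%, of which a fraction c is recorded. With q₁ = c·p₁, q₂ = c·p₂ and q̄ their mean, power (one-sided 0.05, normal approximation) = Φ{[(q₂ − q₁)√126 − 1.645√(2q̄(1 − q̄))] / √(q₁(1 − q₁) + q₂(1 − q₂))}. This gives about 71% for c = 1, 45% for c = 0.5 and 28% for c = 0.25.
- *Unequal loss.* If both arms truly have 5% but one records all events and the other half, the counts are 6.3 and 3.15, an apparent difference where none exists. If the true rates are 2% and 8% but only a quarter of events is recorded in the second arm, both show 2% and a real difference disappears.

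These figures are illustrations. Section 8.2 sets no test, so the power figures describe loss of information and not the behaviour of the monitor's rule.

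**The case against.** The best case for the plan is that it chose targeted collection on purpose and gives its reasons: both tubes are used within their approved indications, and these patients will have many complications of trauma. The important consequences of an insertion injury are collected as outcomes without any attribution. The bar for keeping an event is low, since the possibly related category in 8.3.4 needs only some evidence, even where other factors contributed. The quality assessment nurse receives all complications reported by patients or staff (10.1.4), the day-90 call asks about adverse events (6.3), and the lists in 6.2 and 8.2 are worded as inclusive rather than closed.

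Much of this stands and narrows the point. Some of it does not close the gap. The stated reasons justify leaving out complications of the injury itself, but not complications of the insertion. The plan does not say that the nurse's reports feed the database or a by-arm table. The day-90 call does not lift the 8.3.1 rule.

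Three stronger readings are tempting but unsupported:

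- A reader might infer that insertion injuries and bleeding are lost unless blamed on tube size. They are not, where a listed outcome follows.
- A reader might infer that the monitor cannot apply the stopping criterion. Deaths are captured as outcomes, and many serious complications are listed endpoints; the criterion can be applied, perhaps on incomplete counts.
- A reader might infer a bias towards no difference. That would follow if recording were equally incomplete in both arms, but attribution by someone who knows the tube may differ by arm, and the bias can then go either way.

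**Conclusion.** The point holds in a limited form. The recording rule in 8.3.1 is narrower than the monitoring criterion in 8.2 and the scope used in 8.3.4 and 8.3.7, and three risks that the protocol itself names (site bleeding, lung injury, injury to nearby organs) have no dedicated item. Counts of these events by arm may therefore be incomplete, for the Aim I safety comparison and for the monitor.

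The size of the effect is unknown. It depends on three quantities that the documents do not give: how often these events occur, how many lead to no listed outcome, and how many the principal investigator would call unrelated to tube size. The 1% to 5% range and the recording fractions used above are assumptions. The textual finding rests on none of them.

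The change should be made, because the rule, followed as written, filters safety events on the effect under study, and events not recorded at the time may be hard to recover later.

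**What to change.** 1. Change 8.3.1 so that, in both arms, every AE at least possibly related to the tube or its insertion is recorded, whatever the view on tube size.
2. Add insertion bleeding and injury to the lung or nearby organs to the 6.2 daily log and the 8.2 safety list.
3. Tabulate these events by randomised arm in the reports to the medical monitor.
4. Keep the attribution to tube size as a descriptive field that does not decide whether an event is entered.
5. State 8.3.2 and 8.3.7 as reporting rules only. They may stay narrower than the recording rule; reporting to the IRB need not widen for this purpose.

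The cost is protocol wording and a few REDCap fields. Staff already review charts daily during the hospital stay, so the downside is slightly more event entry. No clinical management changes.

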8.3.2 DEFINITION OF SERIOUS ADVERSE EVENTS (SAE)

A serious adverse event (SAE) is an AE occurring during any study phase (i.e., treatment, follow-up), that results in one or more of the following:

- Death
- Life-threatening adverse event
- Inpatient hospitalization or prolongation of existing hospitalization
- Persistent or significant incapacity or disruption of the ability to conduct normal life functions
- Congenital anomaly/birth defect
- An important medical event that may not result in death, be life-threatening, or require hospitalization but may be considered serious when, based upon appropriate medical judgment, they may jeopardize the patient or subject and may require medical or surgical intervention to prevent one of the outcomes listed above.

In this study, we will only be reporting SAEs that are determined to be unexpected and possibly, probably, or definitely related to the size of the initial thoracostomy tube. The principal investigator will assess all potential adverse events for this criteria.

SAEs will be reported in the manner and timeframe that is outlined in the Chesapeake IRB handbook.

8.3.3 SEVERITY OF EVENT

The Common Terminology Criteria for Adverse Events (CTCAE) v 4.0 developed by the National Institutes of Health's National Cancer Institute will be used as a severity scale for each AE and SAE. The general descriptions of severity for each adverse event is as follows:

Grade 1: Mild; asymptomatic or mild symptoms; clinical or diagnostic observations only; intervention not indicated

Grade 2: Moderate; minimal, local or noninvasive intervention indicated; limiting age appropriate instrumental activities of daily living

Grade 3: Severe or medically significant but not immediately life threatening hospitalization or prolongation of hospitalization indicated; disabling; limiting self-care activities of daily living

Grade 4: Life threatening consequences; urgent intervention indicated

Grade 5: Death related to AE

8.3.4 RELATIONSHIP TO STUDY INTERVENTION

The principle investigator will assess the relationship of an adverse event to the thoracostomy tube insertion procedure or tube size will be the according to the following definitions:

Unrelated	There is no evidence of any causal relationship
Possibly related	There is some evidence to suggest a causal relationship. However, the influence of other factors may have contributed to the event.
Probably related	There is evidence to suggest a causal relationship and the influence of other factors is unlikely
Definitely related	There is clear evidence to suggest a causal relationship and other possible contributing factors can be ruled out.

8.3.5 EXPECTEDNESS

The principle investigator is responsible for assessing the expectedness of an event. Expected safety events of interest for this study include: misplacement of tube, tube migration, death during insertion procedure, air leak, empyema, need for additional interventions (VATS, thoracotomy, chest tube replacement), catheter related blood stream infection and thoracostomy tube related hospital readmission. For the purposes of this study, deaths will be captured as clinical outcomes and do not need to be reported as SAEs unless determined by the principle investigator to be related to chest tube size.

All unanticipated problems that meet study definition will be reported to the IRB. An unanticipated problem is defined as “any serious adverse effect on health or safety or any life-threatening problem or death caused by, or associated with, a device, if that effect, problem, or death was not previously identified in nature, severity, or degree of incidence

in the investigational plan or application (including a supplementary plan or application), or any other unanticipated serious problem associated with a device that relates to the rights, safety, or welfare of subjects" (21CFR 812.3(s)).

8.3.6 TIME PERIOD AND FREQUENCY FOR EVENT ASSESSMENT AND FOLLOW-UP

Participants will be assessed for AEs and SAEs daily during hospitalization and at 90-day follow-up.

8.3.7 SERIOUS ADVERSE EVENT REPORTING

Participants will be monitored for serious adverse events from the moment of randomization through 90 days post tube insertion. Due to their mechanism of injury and high trauma burden, participants are expected to have significant trauma related complications. AEs or SAEs determined to be unrelated to study procedure or tube size will not be reported to the IRB. Submission of any serious adverse event will not occur until relatedness of the event has been determined.

9 STATISTICAL CONSIDERATIONS

9.1 STATISTICAL HYPOTHESES

Primary Efficacy Endpoint(s):

- Aim I
 - Retained hemothorax requiring an additional intervention, either video-assisted thoracoscopic surgery (VATS) or additional thoracostomy tube placement.
- Aim II
 - Empyema rates in traumatic pneumothorax, hemothorax, and hemopneumothorax

Secondary Efficacy Endpoint(s):

- Aim I
 - Duration of chest tube placement
 - Initial drainage from chest tube at 5 minutes
 - Length of hospitalization
 - Subjective pain score (pre- and post-insertion recorded within 5 minutes of insertion). Assessed with 0 -10 numerical pain scale
 - Hemodynamic stability post-insertion (determined by vital signs: temperature, heart rate, blood pressure, oxygen saturation)
 - Time to radiographic resolution of pneumothorax, hemothorax, hemopneumothorax
 - Tube specific complications: Air leak, tube malposition, & tube migration
 - Recurrent pneumothorax/hemothorax/hemopneumothorax after tube removal
 - Readmission to hospital for a chest tube related complication

9.2 SAMPLE SIZE DETERMINATION

Aim I

This study is a non-inferiority randomized controlled trial comparing placement of 14 French vs. 28 French chest tubes for hemothorax and hemopneumothorax. We hypothesize the rate of drainage failure to be approximately 7% in the large 28 tube size group. With a sample size of n=126 per group, we will have 80% power to detect a non-inferiority margin difference between the group rates of 8% (allowing up to a 15% rate of drainage failure in the small 14 tube size group; $\alpha=0.05$). In our prior study, we saw a 20% vs 6.7% difference in needing additional procedures for pneumothorax with small vs large catheters but these numbers are based on draining air not blood. Sample size analyses were conducted in PASS 13⁹.

Aim II

Calculations of sample size were based on two-group comparisons of empyema rates. With assumptions of empyema rate is 5% in the retrospective group and 2% in the prospective group, 586 patients in each group are needed to achieve a power of 0.8 with $\alpha=0.05$. To account for potential attrition, we will inflate the number of patients by 10% resulting in a total of 645 patients in the retrospective group and 645 patients in the prospective group. The sample size was calculated by using the PASS 15¹⁰.

9.3 POPULATIONS FOR ANALYSES

The study population will consist of patients aged 18 and older diagnosed with a traumatic pneumothorax, hemothorax or hemopneumothorax that require non-emergent placement of a thoracostomy tube as part of their care.

9.4 STATISTICAL ANALYSES

9.4.1 GENERAL APPROACH

All analyses for this randomized trial will follow the intention to treat principle with an additional per protocol analysis given the non-inferiority hypothesis. We will first compare the baseline characteristics of the patients by group to assess for statistically significant or clinically meaningful imbalances. If either exists, these factors will be taken into account in sensitivity analyses for the primary and secondary outcomes.

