6.2 INDEX HOSPITALIZATION REVIEW

At the time of enrollment, baseline demographic and injury characteristics will be recorded. Baseline data to be recorded include:

- Demographics (age, sex)
- Vital signs (pre- and post-tube insertion)
- Mechanism of injury (blunt vs penetrating)
- Radiographic findings (pneumothorax, hemothorax or hemopneumothorax)
- Initial laboratory values (hematologic panel, chemistry panel, coagulation panel, toxicology, blood gases)
- Calculated injury severity score

The day of tube insertion will mark study day 0. Subjects will be monitored daily by study staff in the form of chart review for the duration of their hospitalization. A daily data log will be kept for each patient/ The information to be recorded includes:

- Volume of hemo/hemopneumothorax drainage
- Tube misplacement
- Tube migration
- Presence of air leak
- Need for additional thoracostomy tubes

- Need for operative intervention (VATS, thoracotomy)
- Date and time of pneumo/hemo/hemopneumothorax resolution as confirmed by a radiologist
- Date and time of chest tube removal
- Recurrent pnemo/hemo/hemopneumothorax
- Development of infection

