6.4 MEASURES TO MINIMIZE BIAS: RANDOMIZATION AND BLINDING

We will use stratified permuted block randomization with random block sizes to allocate patients in a 1:1 allocation to the 14 or 28 tube sizes. The randomization lists will be generated by a study statistician using SAS Enterprise Guide version 6.1 and stratified by location (Emergency Department and Surgical & Trauma ICU). Randomization lists will be provided to the study coordinator and another study team member not affiliated with clinical care and assessments to place the allocations into number opaque envelopes. These envelopes will be pulled sequentially by the surgeon or study team as a patient is deemed provisionally eligible for the study preserving allocation concealment. The ID of the envelope is recorded in the patient's research record.

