9.4.2 ANALYSIS OF THE PRIMARY EFFICACY ENDPOINT(S)

The rates of failure of drainage (primary outcome) will be estimated as proportions and compared between the two groups using a Chi-square test corrected for the non-inferiority hypothesis. We will present the findings using the difference in the proportions (rate in small group –rate in large group) and corresponding 95% upper confidence limit.

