9.4.3 ANALYSIS OF THE SECONDARY ENDPOINT(S)

Length of stay will be compared using Poisson regression with a main effect of group. Post insertion pain and vital signs will be compared using analysis of covariance controlling for pre-procedural pain and vital signs, respectively, with categorical group effect. We will compare rates of re-intervention and readmission using chi-square tests for independence (or Fisher's exact tests) and present our findings using relative risks and 95% confidence intervals.

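### Covariates for the adjusted sensitivity analyses are chosen from observed baseline imbalance, with statistical significance alone sufficient, and the randomization stratum is in no analysis

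*Combined protocol and SAP*

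**What the plan says.** Section 9.4.1 (General Approach) has the arms compared at baseline "to assess for statistically significant or clinically meaningful imbalances". It continues: "If either exists, these factors will be taken into account in sensitivity analyses for the primary and secondary outcomes". The statistical analysis row of the synopsis (1.1) repeats the rule.

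The analyses around it are:

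- **Primary outcome (9.4.2).** Failure rates are "compared between the two groups using a Chi-square test corrected for the non-inferiority hypothesis" and reported as a risk difference with an upper confidence limit. No covariate enters.
- **Secondary outcomes (9.4.3).** Post-insertion pain and vital signs use "analysis of covariance controlling for pre-procedural pain and vital signs, respectively, with categorical group effect". Length of stay uses Poisson regression with group only. Re-intervention and readmission use unadjusted tests.
- **Randomization (6.4).** Permuted blocks, "stratified by location (Emergency Department and Surgical & Trauma ICU"). Location appears in no analysis in section 9.4.
- **Baseline data (6.2).** "At the time of enrollment, baseline demographic and injury characteristics will be recorded": age, sex, vital signs, mechanism, radiographic findings, five laboratory groups and injury severity score.

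The plan gives no covariate list, no significance level for the baseline tests, no criterion for clinical relevance of an imbalance, and no form for the adjusted model.

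**The concern.** A baseline test compares the arms on a covariate without using the outcome. If randomization is intact, a significant result is a chance event, equally likely for a strong predictor of retained hemothorax and for an irrelevant variable. A rule that admits factors on this basis can bring in noise and will usually pass over variables worth adjusting for.

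The second trigger, clinical relevance, could let prognosis in. It is undefined, however, and applied after the imbalance has been seen, so the adjusted model still depends on the data.

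Location shows the problem from the other side. The design singles it out, and blocking within location keeps it close to balanced, so an imbalance rule will rarely select it.

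What is at stake is the value of the sensitivity analyses. An adjusted result whose covariates were settled after looking at the data is weak evidence that a finding is robust.

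**Working it through.** **1. The plan's own figure.** Inputs from 9.2: 7% failure in the 28 Fr group, margin 8%, 80% power, alpha 0.05. Taking 7% in both arms and a one-sided alpha (9.2 does not state sidedness):

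n = (1.645 + 0.842)² × 2 × 0.07 × 0.93 / 0.08² = 6.18 × 0.1302 / 0.0064 ≈ 125.8, so 126 per group.

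This reproduces the stated size. The calculation contains no covariates, so the selection rule cannot affect it.

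**2. How many baseline tests?** The plan does not say. Two counts from 6.2, taking the vital signs as the four named in section 3 (temperature, heart rate, blood pressure, oxygen saturation):

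- Without laboratory data: age, sex, four vital signs, mechanism, radiographic type, injury severity score = 9.
- With each of the five laboratory groups (hematologic, chemistry, coagulation, toxicology, blood gases) counted once = 14.

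Testing individual analytes within panels could bring the count to 20-25 or more.

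**3. Chance of at least one false flag.** Assuming k independent tests at 5% and intact randomization, P = 1 − 0.95^k; the expected number of flags is 0.05k.

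| k | P(at least one) | Expected flags |
|---|---|---|
| 9 | 37% | 0.45 |
| 14 | 51% | 0.70 |
| 20 | 64% | 1.00 |
| 25 | 72% | 1.25 |

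Positive correlation among vital signs, laboratory values and severity score would generally lower these probabilities.

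**4. Does prognosis affect selection?** In 40,000 simulated trials of 126 per arm, a binary covariate with assumed prevalence 30% was significant at two-sided 5% in 5.0% of trials when labelled non-prognostic and 5.2% when labelled strongly prognostic (failure 4% versus 14%). They agree, as they must, because the test ignores the outcome. By the significance route a strong predictor is left out about 95% of the time.

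**5. What an unflagged imbalance could do.** With the same assumed covariate, the largest imbalance that escapes the test is about 1.96 × √(0.3 × 0.7 × 2/126) = 11.3 percentage points. The shift in the risk difference is then 0.113 × (0.14 − 0.04) = 1.1 points, against a margin of 8. This is a limiting case on assumed figures.

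**6. Room for covariates.** Expected failures at 7% in both arms: 0.07 × 252 = 17.6, about 18. At 7% and 15%: 126 × (0.07 + 0.15) = 27.7, about 28. Treatment, location and two further covariates would put four terms on about 18 events (17.6/4 = 4.4 per term). One further covariate gives three terms (17.6/3 = 5.9 per term).

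**The case against.** The strongest reply is that little depends on this rule. The non-inferiority decision comes from a fixed, unadjusted comparison. The analysis that 9.4.1 adds because of the non-inferiority hypothesis is the per-protocol one, not the adjusted one. Leaving out a predictor that is balanced costs mainly precision when the measure is a risk difference. All of this stands, and it limits the point to supporting analyses.

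Three stronger readings are tempting, and the documents do not support them.

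- A reader might infer that the covariates are set purely by chance. The text has a second, clinical trigger. The fair criticism is that it is undefined and applied after the fact.
- A reader might infer that every outcome lacks prespecified adjustment. The pain and vital-sign ANCOVAs already have fixed baseline covariates, though the rule could add others in sensitivity analyses.
- A reader might infer that the rule would overfit the primary-outcome model. At 20-25 tests only 1.0-1.25 false flags are expected, and a generous prespecified list would strain about 18 events just as much.

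Baseline comparison also has a diagnostic use. Envelopes are drawn at provisional eligibility (6.4), patients with GCS below 15 may be approached up to 24 hours after insertion (1.2, 10.1.1), and screen failures include withdrawals and patients found ineligible after enrollment (5.3). If such losses differ by arm, or in the per-protocol set, imbalance need not be chance. That is a reason to look at the baseline table, which a descriptive presentation allows. It is not a reason to choose covariates by p-value.

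**Conclusion.** The concern holds for the adjusted sensitivity analyses. Significance alone can admit a covariate, the alternative trigger is undefined, nothing is prespecified, and the stratification factor is left out of every analysis. The unadjusted primary test, its type I error and the 126 per group are not affected.

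The chance of at least one spurious covariate is about 37-51% on a plain count of the section 6.2 list (9-14 tests) and 64-72% if 20-25 values are tested. These figures assume independent tests, a 5% level and intact randomization. The count and level are assumptions because the plan gives neither, so the upper range should not be quoted alone.

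This is a modest weakness in supporting analyses. It is worth correcting because a better method is available with data already collected.

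**What to change.** Change section 9.4.1 and the matching synopsis text together.

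- Present baseline characteristics descriptively by arm, and do not use significance tests to choose covariates.
- Replace the imbalance-triggered rule with a sensitivity analysis fixed in advance and run whatever the observed balance.
- **Primary outcome:** a location-stratified risk difference (for example Mantel-Haenszel) with its upper confidence limit against the 8% margin. At most one further collected covariate may be added, with its prognostic rationale stated. Mechanism or injury severity score are candidates, but the documents do not show that either predicts retained hemothorax, so the investigators would need to justify the choice.
- **Secondary outcomes:** adjust for location plus the same prespecified covariate, if one is named, keeping the baseline pain and vital-sign terms already in the ANCOVAs.

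The cost is wording; no new data are needed and the sample size does not change. There is a small downside. With about 18 to 28 failures expected, the list must stay very short, so an imbalance in an unlisted variable would be discussed descriptively or examined in an analysis labelled post hoc.
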